- **Psychoactive Effects (including Drug Liking):** A total of 15 separate VAS ratings will be presented at the time of driving simulation as a 100-mm horizontal line, anchored on the left with 'not at all' and on the right with 'extremely' (Appendix 10). Participants will pencil in a vertical line along the horizontal line that represents their current feeling (questions usually phrased, 'During the past week, did you feel ___ after consuming the vaporized cannabis?'). Ratings will be: any drug effect, a good drug effect, a bad drug effect, high, drunk, impaired, stoned, as if you liked the drug effect, sedated, confused, nauseous, like you desired more of the drug, anxious, down, and very hungry. Similar VAS questions have been shown to be sensitive and reliable subjective measures of cannabis intoxication.¹⁷⁻²⁰ (5 minutes)
- **Pain Relief:** The degree of pain relief after taking the study medication will be assessed by asking the participant to rate if their pain is (1) very much improved (2) much improved (3) minimally improved (4) no change (5) minimally worse (6) much worse (7) very much worse.
- **Pain Score:** Participants will be asked to rate their pain before and after vaporizing marijuana between 0 = no pain and 10=worst possible pain.
- **Driving Simulation Self-Assessment:** This comprises of a total of two questions to be asked hourly. They ask participants to rate how well they did on a VAS scale how well they believe they performed on the driving simulator and how much they believe their ability to perform on the driving simulator was affected by study drug.
- **Driving Test Questionnaire:** This will be administered to evaluate for possible confounding variables on the day of the driving simulation. We will ask the participant how much they slept the previous night and about their experience with computer games.

Sensory Testing

The Cold Pressor Test administered at all study visits will also be administered during driving simulation 3 times at hours 1, 3, and 7 to measure acute effects of pain relief.

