By conducting repeat assessments for four hours following the first vaporization, we will be able to determine at what point participants no longer exhibit acute effects for each of the study medications. Participants will then complete a second vaporization and ingestion of oral medication before hour 6. We will then assess them for three hours in order to determine whether the acute effects are similar to those seen after the first vaporization, or perhaps greater (due to cumulative/residual effects). To minimize the novelty of the driving simulations, participants will complete a pretest training session to re-familiarize themselves with the hardware and the tasks that they are to encounter during the simulations. Four separate tasks will be embedded within the simulation.

Table 3 Assessments of Acute Effects One Day following 2 and 8 Weeks of Cannabis Treatment

Hour	1		2	3	4	5		6	7	8
		Vaporization/Oral Medication					Vaporization/Oral Medication			
Vital Signs	X		X	X	X	X		X	X	X
Numerical Pain Intensity Score	X		X	X	X	X		X	X	X
Cold Pressor Test	X		X					X		
Pain Relief			X	X	X	X		X	X	X
Psychoactive Effects			X	X	X	X		X	X	X
Driving Simulation	X		X	X		X		X	X	X
iPad Performance Testing	X		X	X		X		X	X	X
Blood Draw ($\Delta 9$ -THC levels)	X		X	X	X	X		X	X	X

Driving simulations: Simulation hardware will consist of a 3-screen, wide field-of-view monitor setup, steering wheel, and accelerator and brake pedals. The fully interactive simulations will assess lane tracking (standard deviation of lateral position [SDLP], or “weaving”), response to divided attention stimuli (accuracy, response time), car following, and performance during scenarios simulating routine driving as well as crash avoidance situations.

Participants in the simulator study will also be assessed for far visual acuity (Snellen Visual Acuity eye chart; need to have acuity of 20/40 or better, with or without correction), color vision, and contrast sensitivity (Vistech Contrast Sensitivity (Pelli-Robson Chart)). Participants will complete an orientation and practice drive prior to the initial simulation, in order to familiarize them with the controls and roadways.

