4.2.3 Comparison of subjective and psychoactive side effects between treatment arms

Psychoactive effects will be assessed at 1, 2, 3, 4, 5, and 6 hours after the first acute administration of treatment at the driving simulation visit in a substudy. Area under the time concentration curve (AUC) will be used as a measure for the aggregate effect of response over a period of time (during 1-6 hours after the 1st dose). AUC will be compared between the arms using linear regression (Aim 2).

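### The driving-visit psychoactive ratings ask for current feeling but use a past-week stem naming only the vaporized product, which does not fit the hourly schedule, the AUC or the double-dummy design

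*Protocol*

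**What the plan says.** Protocol section 9, Arm #2 (Driving Simulation), under Psychoactive Effects, states: "A total of 15 separate VAS ratings will be presented at the time of driving simulation". The response instruction is: "Participants will pencil in a vertical line along the horizontal line that represents their current feeling". A parenthesis in the same sentence then describes the items, which it says are usually phrased as "During the past week, did you feel" a given effect "after consuming the vaporized cannabis". The form itself is Appendix 10, which is not among the documents available.

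Table 3 of the protocol schedules these ratings at Hours 2 to 8, with none at Hour 1 before dosing. Vaporized and oral medication are taken together twice, before Hour 2 and before Hour 6. The text above the table says that the repeat assessments are meant to show "at what point participants no longer exhibit acute effects for each of the study medications".

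SAP 4.2.3 states: "Psychoactive effects will be assessed at 1, 2, 3, 4, 5, and 6 hours after the first acute administration of treatment". It summarizes them by an AUC, described as a measure of the "aggregate effect of response over a period of time (during 1-6 hours after the 1st dose", and compares the arms by linear regression. SAP 4.2 lists these effects as secondary outcomes of the driving substudy and ranks vaporized cannabis (arm A) against dronabinol (arm B) as the first comparison.

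**The concern.** Two features of the stem do not suit its use.

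**Time frame.** A rating repeated every hour, and integrated over the hours after a dose, has to ask about the present moment. A question about the past week, put to someone who has just finished eight weeks of home dosing, asks largely about that home use.

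**Product.** The trial is double-dummy. In arm B the inhaled product is placebo and the active drug is the capsule. A question about effects of the vaporized product points toward the active route in arm A and away from it in arm B, and A versus B is the first-ranked contrast.

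At stake is the only scheduled hourly self-report of effects such as feeling high or stoned, which SAP 4.2.3 assigns to Aim 2. If the wrong period or product has been rated, no later analysis can recover the intended measurement.

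**Working it through.** The documents give no figure for this point, so the check sets the texts side by side.

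| Source | Period implied | Product implied |
|---|---|---|
| Protocol 9, response instruction | now | none named |
| Protocol 9, usual stem | past week | vaporized only |
| Protocol 9, Table 3 | each hour, Hours 2 to 8 | both, taken at the same two dosing events |
| Protocol 9, stated purpose of the repeats | until acute effects end | each study medication |
| SAP 4.2.3 | 1 to 6 h after first dose | assigned treatment |

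The usual stem disagrees with the other four rows on period. On product it disagrees with the last three.

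1. **Number of answers affected.** Table 3 marks 7 time points (Hours 2, 3, 4, 5, 6, 7, 8). With 15 items, that is 7 × 15 = 105 marks per participant.

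2. **What the AUC becomes under the past-week stem.** Assume hourly ratings r1 to r6 and the trapezoidal rule, which the SAP does not specify. Then AUC = r1/2 + r2 + r3 + r4 + r5 + r6/2. If the answer describes the week and stays at one value c, AUC = c/2 + 4c + c/2 = 5c. That is a single recall rating multiplied by five, with no information on onset or recovery. This is the limiting case. The past week can include the day of the visit, so the answers need not be flat.

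3. **What the product wording does in arm B.** Protocol section 18 puts the oral peak at 1 to 6 hours after ingestion, and SAP 4.3.2 expects dronabinol effects to be delayed relative to whole-plant cannabis. An oral effect may therefore come on at a time that a participant does not connect with inhaling. Two responses are possible: (a) the participant believes the vapour was inert and marks little or nothing despite feeling the capsule; or (b) the participant, blinded and dosed with both products at once, credits the vapour and marks the effect in full. Response (a) lowers arm B and (b) does not. The documents give no basis for the split between them.

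4. **Whether other wording was available.** At the same visit the pain-relief item asks about the study medication, and the driving self-assessment asks about the study drug. Both are product-neutral. For the M-scale at study visits, the protocol deliberately rewords the items to the past week instead of the acute response. The authors thus distinguish the two frames elsewhere.

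5. **Possible origin (inference only).** The scale's appendix number (10) and references (17 to 20) fall within the numbering of the study-visit instruments: Appendices 9 and 11, references 16 and 21. That would be consistent with a study-visit item moved to the driving session without rewording. The documents do not say so.

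**The case against.** The strongest reply is that the protocol instructs participants to mark how they feel at present and gives the stem only as the usual phrasing. The form is not available. If it carries momentary wording, or if participants follow the instruction, the ratings can follow the time course. This stands. The protocol text is self-contradictory; it does not specify pure past-week recall.

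Second, everyone inhales and takes capsules at the same dosing events under blinding, so any feeling after the vapour is also a feeling after the capsule. This stands too. A reader might infer that dronabinol effects are under-recorded and that A versus B is tilted toward vapour. The documents show only that this could happen. Assuming that, say, 20% to 50% of arm B discounts oral effects, and reading off an understatement of the same size, merely restates the assumption.

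Third, these ratings do not carry Aim 2 alone. The M-scale is also a secondary outcome and is analysed over the six study visits, and the driving visit has hourly self-assessment, performance tests and blood THC. This limits the consequence. It does not remove it, because the M-scale asks about the past week by design and the other measures do not grade the same subjective effects hour by hour.

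None of these replies explains why a past-week, vapour-only stem appears in the description of an hourly acute rating.

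**Conclusion.** The wording is wrong as written and should be corrected. The protocol contradicts itself on the period rated, and the usual stem fits neither the hourly schedule and its stated purpose nor the AUC in SAP 4.2.3. It also names one of two study products in a double-dummy trial. If the stem is used as written, the ratings may not track the acute time course and may miss or misattribute oral dronabinol effects.

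No size can be given. The direction of any A versus B bias is also undetermined, because it depends on how blinded participants attribute effects. A reader might go further and infer that the ratings cannot show acute effects at all, or that the acute part of the AUC is zero in every arm. That would require the past-week stem to be on the form, to be answered literally, and to exclude the visit day; the documents establish none of these.

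The consequence is confined to a secondary outcome in the driving substudy, for which SAP 5.1 plans 29 per arm. The primary pain endpoint is untouched.

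**What to change.** Check the Appendix 10 form against Protocol section 9, then bring both to one momentary, product-neutral stem for the driving visit. Examples are 'Right now, do you feel [effect]?' or a version that refers to the study medication. Keep any past-week version for study visits only, where it would sit alongside the M-scale.

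The cost is one form revision and a matching protocol edit, with no added visit time and no change to the planned AUC comparison. The one complication is timing: the microbiome section of the protocol describes the trial as ongoing. If the past-week stem has already been used, record which form version each participant completed. The SAP should then say, before unblinding, how version will enter the AUC analysis (for example as a covariate, or by analysing the versions separately) and how AUCs from the old stem will be interpreted. If the form already carries momentary, neutral wording, only the protocol sentence needs correcting.

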4. ESTIMATED DURATION OF THE STUDY

We estimate that the study will take 4 years.

5. LAY LANGUAGE SUMMARY OR SYNOPSIS (no more than one paragraph)

This study will involve treating low back pain associated with nerve injury with two types of medicinal cannabis for eight weeks. Research subjects will consume either oral Δ9-THC (dronabinol), vaporized 4.0% Δ9-THC/6.5% CBD (estimated percentages), or placebo. An analysis will then be performed to assess the risk-benefit ratio of dronabinol and vaporized 4.0% Δ9-THC/6.5%. In addition, subjects will undergo driving simulation to determine how long it takes for them to recover from these medications.

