Both of the above studies were 6-hour human laboratory experiments. The present study is designed to evaluate whether or not the medium dose of cannabis (3.5%) can maintain an analgesic response over an eight-week period. In addition, a direct comparison of this vaporized preparation will be made with dronabinol and placebo. The medium dose of cannabis (3.5%) has been selected as it was utilized in a human experimental laboratory experiment that compared inhaled Δ9-THC and dronabinol.⁶ Using the cold-pressor test, participants immersed their hand in cold water (4 degrees C), and the time to report pain (pain sensitivity) and withdraw the hand from the water (pain tolerance) was recorded. Compared with placebo, marijuana and dronabinol decreased pain sensitivity, increased pain tolerance, and decreased subjective ratings of pain intensity. The magnitude of peak change in pain sensitivity and tolerance did not differ between marijuana and dronabinol, although dronabinol produced analgesia that was of a longer duration. Marijuana and dronabinol also increased abuse-related subjective ratings relative to placebo; these ratings were greater with marijuana. These data indicate that under controlled conditions, marijuana and dronabinol decreased pain, with dronabinol producing longer-lasting decreases in pain sensitivity and lower ratings of abuse-related subjective effects than marijuana.

A direct comparison of cannabis and dronabinol has not been performed in a clinical population. The present study will fill this void by performing a randomized, double-blind placebo controlled 8-week trial comparing the effectiveness of oral versus vaporized cannabis in patients with chronic low back pain. In addition to studying efficacy, we will also perform a driving simulation study to determine the real-world impact of cannabinoid treatments.

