- Preventing children and adolescents from gaining access to medicinal cannabis because of potential harm to their well-being. Subjects will be required to store cannabis in an area of their home that would prevent anyone else from discovering its location.
- Because some people cannot control their use of cannabis, we will not allow patients with recent substance abuse histories (less than 12 months) to participate.
- We will exclude patients if they are pregnant or refuse to exercise birth control if engaging in sexual activities that could result in pregnancy, have a heart disease or heart rhythm problem or have a history of serious mental illness (e.g., schizophrenia, mania, or a history of hallucinations or delusions)
- In order to avoid carcinogens, we will have subjects use a vaporizer rather than smoke joints or use a water pipe.

- We will instruct subjects not to drive a car or operate heavy machinery for 3-4 hours after use of medicinal cannabis, or longer if larger doses are used or the effects of impairment persist. They will use a designated driver for automobile transportation if they have to go out sooner than 3-4 hours after taking this medicine.
- As the response to cannabis varies widely, participants will titrate to effect and in essence use the minimum amount of medicinal cannabis needed to obtain relief from pain.
- A cannabis withdrawal syndrome will be under surveillance for two weeks; difficulty with getting to sleep and angry outbursts might require that they withdraw from the cannabis more slowly.

The UCSD Department of Psychiatry (Appendix 17) is committed to providing the resources and other supports (e.g., data management and information systems, statistical, and physical performance site) to ensure the timely implementation, conduct, and completion of this program.

Data and Safety Monitoring Board (DSMB)

A DSMB will be selected utilizing a group of experts that will advise the study investigators, with the primary responsibility to monitor human subject safety. The members will be comprised of at least 3 independent clinicians familiar with the conduct of clinical trials. The DSMB will consider study-specific data as well as relevant background information about the test agents and target population under study. The DSMB will review the protocol, including the safety monitoring plan, and identify any major concerns prior to implementation. During the trial the DSMB will review:

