18. RISK/BENEFIT RATIO

There is a substantial disconnect between the therapeutic use of cannabis and research on the risks and benefits of this practice. Although edible marijuana merchandise has become widely available at medical dispensaries, there is little information in the literature on the medical efficacy of these products ⁶². Pharmacologic oral preparations, which like the edible products, avoid deleterious effects upon the respiratory system, have had more attention from the scientific community ⁶³⁻⁶⁹. However, some experts have opined that whole plant cannabis is superior to the FDA approved oral cannabinoid preparations, e.g., synthetic tetrahydrocannabinol (dronabinol, Marinol®) and/or the synthetic analog of Δ9-THC (nabilone, Cesamet®). As testament to this belief, oral cannabinoids have been on the market in the United States for many years and are not widely used ⁷⁰. Peak plasma concentrations occur 1 to 6 hours after ingestion, with a magnitude approximately 10% of that achieved with smoking ⁷¹. As a result of the pharmacokinetics of oral preparations, it has been postulated that the preference expressed by patients for herbal cannabis is a result of the faster onset and shorter duration of action allowing titration of dose to the desired effect ⁷². The present study will compare the risk benefit ratio of herbal cannabis to an oral preparation (dronabinol). We know that cannabinoids appear to have some benefit in alleviating a heterogeneous collection of neuropathic pain conditions ^{2, 3}. Preliminary recommendations have been issued from the College of Family Physicians in Canada to help guide clinicians in prescribing cannabis for the treatment of for chronic noncancer pain ⁷³. But we do not know if chronic low back pain will respond to cannabis (or dronabinol).

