4.2.4 Comparison of driving performance between treatment arms

The driving simulation assessments will be conducted in the substudy. (1) Driving measurements (standard deviation of lateral deviation (SDLP) for lane tracking and coherence for car following) following 8 weeks of study medication administration will be compared between treatment arms using ANOVA, to determine whether driving skills will be different after stable cannabis treatment. Acute cannabis effects will be then tested using a covariance pattern model (e.g., unstructured model) including fixed effects of treatment arm, time (minutes), and their interaction. (2) We will also include terms for pain (separately using intensity and relief), its interaction with treatment, and time too, the latter to test for recovery of the cannabis effect back to the Hour 1 baseline level. (3) The correlation (Pearson or Spearman, as appropriate) between blood $\Delta 9$ -THC and each of SDLP and coherence will be estimated at each hour using a 95% confidence interval applied to the Fisher Z-transformation, then back-transformed. Secondary analyses will use independent t-tests or Wilcoxon rank sum tests to compare differences between the means of each of coherence and SDLP for high and low blood $\Delta 9$ -THC levels split at 7 ng/ml. (Aim 3)

4.3 Exploratory analysis:

4.3.1 We will assess the association of daily pain intensity and the dose of treatment (mean daily number of puffs or pills) using a mixed-effects model including fixed effects of dose, treatment regimen, time (i.e., day or week), and dose x treatment regimen interaction, and subject-specific random effect. A significant interaction indicates the association of the dose and pain intensity differs in the three treatment arms. Use of breakthrough pain medication will be then included in the model to remove its confounding effect if it's present. A Non-significant interaction will be removed from the models.

- 4.3.2 Cumulative distributions of maximal pain reduction from baseline among treatment groups will be compared using Kolmogorov-Smirnov tests. This test (nonparametric) will indicate if a given treatment is likely to produce more overall pain reduction than another treatment regimen and takes into account an expected delay in effects of dronabinol compared to whole plant cannabis.

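### Time to recovery of driving is not assured for dronabinol: the last driving test before re-dosing is 3 to 4 hours after the oral dose, inside the protocol's 1 to 6 hour range for the oral plasma peak

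*Protocol*

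**What the plan says.** Recovery time is a stated purpose of the driving session. The lay summary (protocol section 5) says that "subjects will undergo driving simulation to determine how long it takes for them to recover from these medications". Section 9, Arm #2, gives the method: "By conducting repeat assessments for four hours following the first vaporization", it says, "we will be able to determine at what point participants no longer exhibit acute effects for each of the study medications". It continues: "Participants will then complete a second vaporization and ingestion of oral medication before hour 6". Three further hours of assessment are then meant to show whether the second dose acts like the first or adds to it.

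In Table 3 the first vaporized and oral dose falls between Hours 1 and 2, and the second between Hours 5 and 6. Driving is tested at Hours 1, 2, 3, 5, 6, 7 and 8, so not at Hour 4. Blood THC is drawn at every hour.

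SAP 4.2.4 models acute effects by arm, time in minutes and their interaction. It then adds pain and time terms, "the latter to test for recovery of the cannabis effect back to the Hour 1 baseline level".

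On the timing of oral products:
- Protocol section 18: "Peak plasma concentrations occur 1 to 6 hours after ingestion".
- Protocol section 7, on a laboratory cold-pressor study: "dronabinol produced analgesia that was of a longer duration".
- SAP 4.3.2 chooses a test for pain reduction partly because dronabinol is expected to act later than inhaled cannabis.

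Section 15 states: "We will instruct subjects not to drive a car or operate heavy machinery for 3-4 hours after use of medicinal cannabis". The same sentence allows for a longer period with larger doses or persisting impairment.

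**The concern.** The promise covers every study medication, but one schedule serves an inhaled and an oral product whose time courses the documents themselves expect to differ. A dronabinol participant whose effect develops late may match the Hour 1 level at Hours 2, 3 and 5 because the effect has not yet developed. The second dose then makes it impossible to see the first dose wear off.

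The SAP does not guard against this. It does not define recovery, does not require that worsening be shown first, has no term for the second dose, and does not say how participants still affected at Hour 5 are handled. At stake is whether a published recovery time for dronabinol, or a ranking of the two products on recovery, would mean what it says.

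**Working it through.** **Inputs.** From Table 3 and section 9: first dose between Hours 1 and 2; second dose between Hours 5 and 6; driving tests before the second dose at Hours 2, 3 and 5. From section 18: oral plasma peak at 1 to 6 h. From SAP 5.1: 29 participants per arm in the driving substudy.

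**1. The plan's four hours.** Time since the first dose at Hour 5 = 5 − dose time.

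| First dose given | Driving tests, hours after dose | Undisturbed window |
|---|---|---|
| Just after Hour 1 | 1, 2, 4 | 5 − 1 = 4 h |
| Midway | 0.5, 1.5, 3.5 | 5 − 1.5 = 3.5 h |
| Just before Hour 2 | 0, 1, 3 | 5 − 2 = 3 h |

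The stated four hours is reproduced as the maximum. It also matches a count of four hourly assessments (Hours 2 to 5), although driving is tested at only three of them.

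**2. Window against the stated peak range.** The window ends 6 − 4 = 2 h to 6 − 3 = 3 h before the latest stated plasma peak. The part of the 1 to 6 h range left uncovered is (6 − window)/(6 − 1):
- 4 h: 2/5 = 40%
- 3.5 h: 2.5/5 = 50%
- 3 h: 3/5 = 60%

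**3. Share of participants.** The documents give no distribution of peak times, so each line below is an assumption.
- Uniform over 1 to 6 h: 40% to 60%. Of 29 participants, 0.40 × 29 = 11.6 to 0.60 × 29 = 17.4, so about 12 to 17.
- Triangular over 1 to 6 h with mode m: the share peaking after window w is (6 − w)²/[5(6 − m)] if w ≥ m, and 1 − (w − 1)²/[5(m − 1)] if w < m. At w = 4, m = 1 gives 4/25 = 16% and m = 4 gives 4/10 = 40%. At w = 3, m = 1 gives 9/25 = 36% and m = 4 gives 1 − 4/15 = 73%.

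These are shares of plasma peaks. Recovery needs a peak and then a decline, so if impairment follows plasma level, more recoveries than this would go unseen.

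**4. Whether later hours help.** Hour 8 is 8 − 2 = 6 h to 8 − 1 = 7 h after the first dose, but the second dose intervenes. The second dose is itself followed for only 8 − 6 = 2 h to 8 − 5 = 3 h.

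**5. Direction of bias.** An effect that develops after Hour 5 makes dronabinol look unimpaired or already recovered in the first window. A residual first-dose effect added to the second dose, in a model that does not separate them, makes it look worse or slower to recover at Hours 6 to 8. The documents do not show which would dominate.

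**The case against.** A reader might infer that recovery time cannot be determined at all for dronabinol, that recovery will be declared before peak effect, and that the error must make oral THC look safer for driving. The documents do not support that much.

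- The lower part of the peak range lies inside the window. Participants who peak early and return by Hour 5 can be observed.
- The 1 to 6 h figure is plasma concentration for oral preparations, not driving impairment. The longer duration in section 7 concerns analgesia, and the delay expected in SAP 4.3.2 concerns pain and has no figure. No document gives a time to onset or peak of driving impairment, so a late effect is a reasonable inference and not a documented fact.
- The bias can run either way, as shown above.
- Section 9 ties recovery to the hours before the second dose and gives the later hours a separate purpose. The arm-by-time interaction lets arms differ in time course, and hourly THC levels could show who was still rising at Hour 5.
- The instruction in section 15 is not a fixed limit, and no document says that the study is meant to validate it.
- Aim 3 is to compare acute effects on driving between arms. It does not mention recovery time, and driving is a secondary outcome.

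These points limit the claim but do not remove it. The separation of first- and second-dose hours in section 9 is not carried into SAP 4.2.4. A contrast of Hour 5 with Hour 1 would be possible if time were a factor, but it is not specified. SAP 4.2.4 correlates THC with driving at each hour, but nothing uses THC to qualify a recovery statement. The wording for each medication remains broader than the schedule can support.

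**Conclusion.** The concern holds in this form: the session does not assure a time to recovery for dronabinol. That time is right-censored for participants who peak or remain affected after about 3 to 4 h, and a match to Hour 1 by Hour 5 may reflect an effect that has not yet developed. SAP 4.2.4, followed as written, can misreport recovery in either direction.

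The mismatch between the 3 to 4 h window and the 1 to 6 h range follows directly from the documents. Its size in participants does not: 40% to 60% rests on an assumed uniform distribution, the wider 16% to 73% on assumed triangular shapes, and both on plasma peak standing in for effect.

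The Aim 3 comparison of acute effects between arms within the observed window is still possible, and the primary pain analysis is not touched.

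**What to change.** Amend protocol sections 5 and 9 and SAP 4.2.4 before the driving data are analysed:

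1. Estimate recovery from Hours 1 to 5 only. Analyse Hours 6 to 8 separately as the second-dose effect.
2. Conclude recovery in an active arm only where worsening from Hour 1 was first shown and then returned. Otherwise report recovery as not reached, censored at Hour 5. Use the planned hourly THC levels to flag participants still rising at Hour 5.
3. State that for dronabinol the session gives at most a lower bound on recovery time, and do not rank the two products on it.

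The sponsor should also reconcile the session dosing times in section 9, the no-driving instruction in section 15 and the 1 to 6 h figure in section 18. Which of them should change is a clinical decision, outside this point.

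The cost is protocol and SAP wording, with no extra visits and no change of schedule. The downside is that the dronabinol recovery statement becomes a bound and not a time.
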